1. PROTOCOL SUMMARY

1.1. Synopsis^a

A Phase 2a Randomized, Double-blind, Placebo-Controlled, Parallel-Group, Multi-center Study Investigating the Efficacy, Safety, Tolerability and Pharmacokinetics of JNJ-67953964 in Subjects with Major Depressive Disorder.

JNJ-67953964, previously known as Cerecor (CERC)-501 and LY2456302, is a small molecule, high-affinity, selective kappa opioid receptor (KOR) antagonist. JNJ-67953964 is orally bioavailable and suitable for once-daily (QD) administration.

KORs and their native ligand dynorphin are localized in areas of the brain that effect reward and stress and may play a key role in mood, stress, and addictive disorders. Chronic stress, substance abuse, and acute withdrawal lead to increased dynorphin expression, activating KORs and subsequent downstream signaling pathways to inhibit mesolimbic dopamine surge, contributing to negative affective states. The behavioral pharmacology of KOR antagonism has been tested in animal models of anhedonia, depression, and anxiety and found to have meaningful effects that may translate to therapeutic benefit in humans. KOR antagonists may be effective for the treatment of patients with mood disorders, perhaps by modulating the negative affective state associated with stress response.

Only about 50% of patients with major depressive disorder (MDD) show a meaningful response (>50% improvement to a first line antidepressant treatment), leaving many patients with substantial persistent impairment. Therapeutic strategies such as switching antidepressants and using adjuvant drug treatments can improve response, however almost 40% of patients remain symptomatic and fail to achieve full remission. Recently, Alkermes (ALKS) 5461, a combination of buprenorphine, which is a partial μ -opioid receptor agonist and KOR antagonist, and samidorphan, a potent μ -opioid receptor antagonist, has been tested in Phase 2 trials in subjects with MDD who have had only a partial response to treatment with a selective serotonin reuptake inhibitor (SSRI) or a serotonin-norepinephrine reuptake inhibitor (SNRI). Adjunctive treatment with ALKS 5461 was associated with greater symptom reduction compared to placebo, suggesting that a KOR antagonist could provide a meaningful clinical benefit for patients being treated for MDD.

OBJECTIVES AND HYPOTHESIS

Primary Objective

The primary objective of this study is to evaluate the efficacy of JNJ-67953964 compared to placebo when administered as adjunctive treatment in subjects with MDD partially responsive to SSRI/SNRI treatment in terms of reduction of symptoms of depression, as assessed by the change from baseline on the Montgomery Asberg Depression Rating Scale (MADRS) in non-responders during the placebo lead-in period.

^a This section has been amended by amendment INT-1

Secondary Objectives

The secondary objectives of this study are:

- To evaluate the efficacy of JNJ-67953964 compared to placebo when administered as adjunctive treatment in subjects with MDD partially responsive to SSRI/SNRI treatment in terms of reduction of symptoms of depression, as assessed by the change from baseline on the Montgomery Asberg Depression Rating Scale (MADRS) in both responders and non-responders during the placebo lead-in period.
- To investigate the overall safety and tolerability of treatment with adjunctive JNJ-67953964 in subjects with MDD when used in combination with a SSRI or SNRI.
- To investigate the effect of JNJ-67953964 versus placebo on depression related anhedonia as assessed by the Snaith-Hamilton Pleasure Scale (SHAPS).
- To investigate the effect of JNJ-67953964 on symptoms of depression using the Clinical Global Impression-Severity (CGI-S), the patient reported Symptoms of Major Depressive Disorder Scale (SMDDS) and the self-assessment of treatment experience (SATE).
- To investigate the effect of JNJ-67953964 on symptoms of anxiety using the Hamilton Anxiety Scale (HAM-A) and on core symptoms of anxiety using the HAM-A₆ subscale.
- To assess the plasma pharmacokinetics (PK) of JNJ-67953964 in subjects with MDD and explore its relationship with efficacy and safety parameters.

Exploratory objectives:

- To explore the effect of JNJ-67953964 on aspects of cognitive and executive function using the Cognitive and Physical Functioning Questionnaire (CPFQ).
- To explore mood-related biomarkers (including but not limited to growth factors, hypothalamic–pituitary–adrenal [HPA] axis markers, immune system activation, metabolic markers) and genetic/epigenetic variation that may be related to clinical response, nonresponse, or safety and tolerability parameters of JNJ-67953964.

Hypothesis

The primary hypothesis is that 6-weeks of adjunctive treatment with JNJ-67953964 is superior to placebo in improving symptoms of depression, as measured by the change from baseline in the MADRS, in subjects with MDD who are partially responsive to SSRI/SNRI treatment.

OVERVIEW OF STUDY DESIGN

This will be a multi-center, placebo-controlled, randomized, double-blind study in subjects with MDD who have had inadequate response to SSRI/SNRI treatment. Approximately 142 subjects will be included in the study.

For each subject, the study will consist of two phases: a screening phase of up to 5 weeks and a double-blind treatment phase lasting 11 weeks.

Subjects with MDD who have had treatment initiated with an SSRI/SNRI allowed by the protocol and have had an inadequate or only partial response to this treatment will be screened at

[figure not shown]
the investigational site. Assessments by qualified site personnel including the MINI, Antidepressant Treatment History Questionnaire (ATRQ, Chandler 2010), and MADRS will be audio recorded at screening for review of eligibility of the subject for enrollment into the study by an independent central reviewer contracted by the sponsor. The following key inclusion criteria/assessments will be reviewed by a central independent reviewer: the clinical history of MDD, SSRI/SNRI treatment of adequate dose and duration for the current episode of depression, and current symptom severity on the MADRS. In case of discrepancy of central reviewer and local rater, the central reviewer will discuss the discrepancy with the local rater. If the discrepancy persists, the local rater will overrule central review.

If 2 weeks or more elapse between the MADRS rating at screening and Visit 2, the local rater will complete the MADRS again by a telephone interview up to 4 days before Visit 2 to determine whether the subject still meets the thresholds for inclusion.

Subjects who meet the inclusion and exclusion criteria and are enrolled will be maintained on the SSRI/SNRI without change throughout the study to determine whether adjunctive treatment with JNJ-67953964 can reduce symptoms of MDD.

The treatment phase of the trial will consist of 3 periods. A placebo lead-in period of concealed duration, after which subjects will enter the double-blind treatment period when they will be randomly assigned to 10 mg JNJ-67953964 or continue placebo for 6 weeks. Subjects who complete the treatment period, will then enter the withdrawal period and be treated with placebo for the remaining time of the treatment phase of the study. The total study duration for each subject will be approximately 16 weeks. There will be 11 scheduled visits to the clinical research center including screening during the study. An overall flow diagram of the study is shown in Figure 1.

Figure 1: Flow diagram of the study

Eligibility Screening Examination

After giving written informed consent, subjects will be screened within 35 to 2 days prior to Day 1 to ascertain their eligibility for the study per the inclusion and exclusion criteria. Upon completion of all informed consent form (ICF) procedures, recording of adverse events (AEs) and concomitant medication will start. Each subject in this study must have their current study participation status checked by a clinical trials verification system when such a system is available for this study.

The symptoms of depression will be assessed using the (structured interview guide for the) MADRS.

Double-blind Treatment Phase

The duration of the double-blind treatment phase will be 11 weeks divided into 3 periods. Subjects will visit the study center for baseline visits on Day 1. The subject will receive study medication after completion of the visit on Day 1. The first dose will be taken at home on Day 2.

Medication will be dispensed at each study visit during this double-blind period. All study medication will be taken in fasting condition.

During the double-blind study phase, the subjects will visit the study center for out-patient visits every 1 to 2 weeks as indicated in the [Time and Events Schedule \(TES\)](#).

Lead-in period

Subjects who successfully complete the baseline examination visit at the clinical site/unit, will be treated with placebo for the entire duration of the lead-in period. Investigators and subjects will be blinded to the exact duration of lead-in period for each subject in the study.

Treatment period

At the end of the lead-in period both placebo lead-in responders and placebo lead-in non-responders will be randomized to receive either placebo or 10 mg JNJ-67953964 in a 1:1 ratio for 6 weeks. Investigators and subjects will remain blinded to exact timing of the randomization, response criterion and study drug treatment assignment for each subject.

Withdrawal period

Subjects who complete the double-blind treatment period prior to the end of Week 11 will enter the withdrawal period where they will be treated with placebo for the remaining time of the treatment phase of the study. Investigators and subjects will be blinded to the exact duration of withdrawal period for each subject in the study.

Early withdrawal visit

Subject who prematurely withdraw from the study are encouraged to complete Visit 11. The procedures to be completed during this visit are listed in the TES.

SUBJECT POPULATION

Approximately 142 subjects with MDD who have inadequately responded to a SSRI/SNRI will be enrolled in this study.

Subjects will be enrolled after reading the subject information sheet and signing the ICF indicating that they understand the purpose of and procedures required for the study and are willing to participate in the study and comply with the study procedures.

DOSAGE AND ADMINISTRATION

JNJ-67953964 will be supplied for this study as 5-mg capsules. Placebo will be supplied as matching capsules.

All subjects will take 2 capsules QD. The capsules will be taken daily from Day 2 to Day 78 (at home and when being in the clinic) in fasting condition with some water (fasting for at least 4 hours before dosing; water intake is permitted during that period). Study medication will be taken before breakfast. If the subject has forgotten to take the study medication before breakfast, this should be done before the next following meal, at the latest at dinner of the same day. If the subject remembers later than dinner, the dose of that day should be omitted, and the subject should take his dose before breakfast on the next day.

The capsules must be swallowed whole and not chewed, divided, dissolved or crushed. After having taken the study medication, subjects should try not to eat or drink for at least 30 minutes. This period should be controlled when the subject is in the clinic. When outside the clinic, violation of this effort (including drug intake in fasting condition) will not be considered a protocol violation.

The first dose will be taken in fasting condition on Day 2 of the double-blind phase when the subject is at home.

The subjects will take the study medication with them at each study visit and will take study medication - from the blisters dispensed at the previous study visit - at the site in fasting condition after completion of predose study assessments and blood collections. Dosing will be witnessed by the study staff.

The dose of the study medication is:

- 10 mg JNJ-67953964: 2 capsules of 5 mg JNJ-67953964
- Placebo: 2 placebo capsules.

Study medication dose may be adjusted to 5 mg QD based on the results of a blinded review of the safety data by the study responsible physician (SRP) or by an unblinded review by the Data Review Committee (DRC) or a physician who is not a member of the study team (See Section 7.1). When a dose reduction has been decided on, this will only apply to new subjects in study and the dose of study medication will be:

- 5 mg JNJ-67953964: 1 capsule of 5 mg JNJ-67953964
- Placebo: 1 placebo capsule.

EVALUATIONS OF EFFICACY

Clinician rated measures for depression

- *Montgomery–Åsberg Depression Rating Scale (MADRS)*
- *Clinical Global Impression scale - Severity of Illness (CGI-S)*

Patient rated measures for depression

- *Symptoms of Major Depressive Disorder Scale (SMDDS)*
- *The Self-Assessment of Treatment Experience (SATE)*

Patient rated measure for anhedonia

Snaith–Hamilton Pleasure Scale (SHAPS)

Clinician rated measures for anxiety

- *Structured Interview Guide for the Hamilton Anxiety scale (SIGH-A)*
- *HAM-A6. The HAM-A6 is a 6-item subscale derived from the original HAM-A.*

Patient rated measure for cognition

Cognitive and Physical Functioning Questionnaire (CPFQ).

PHARMACOKINETIC EVALUATIONS

Venous blood samples of 6 mL will be collected for determination of JNJ-67953964 plasma concentrations and metabolites when required specified in the TES. In addition, some samples may be used to measure plasma concentrations of the SSRI/SNRI used by the subject.

A PK blood sample will be collected at the same time as the blood samples for biomarkers when indicated in the TES.

BIOMARKER EVALUATIONS

During the study, blood and saliva will be collected for the assessment of biomarkers at the time points indicated in the TES.

In blood and/or saliva, biomarkers related to the HPA axis activation including but not limited to adrenocorticotrophic hormone (ACTH) and cortisol, neurotropic factors, inflammation and metabolic factors may be investigated.

Biomarker essays may be added or deleted based on scientific information or technical innovations under the condition that the total volume of blood collected will not be increased.

The biomarker evaluations will include blood collection for genetic/pharmacogenomic and epigenetic testing to characterize gene expression in relation MDD symptoms and biomarker results. Participation in the genetic/pharmacogenomic part of this study is mandatory.

SAFETY EVALUATIONS

The collection of AEs and concomitant medications will start after the ICF has been signed and will continue until the final visit. AEs of special interest include pruritus and gastrointestinal (GI) complaints such as dyspepsia, abdominal pain, constipation, or diarrhea. If these are of moderate or severe intensity (sufficient discomfort to cause interference with normal activity and/or warrant treatment), investigators should provide a narrative to describe the event. At a minimum, a description of the event (including any known precipitating circumstances), the time relative to dose administration, the duration, concomitant treatment, and outcome of the event will be reported.

Apart from this, the following safety assessments will be done: physical examination, neurological examination, body weight, vital signs (including temperature), 12-lead electrocardiogram (ECG), urine drug testing, pregnancy testing (female subjects only), clinical labs (hematology, chemistry panel, gastric mucosa integrity panel) and urinalysis. At screening only: serology, thyroid function, and HbA1c (diabetic subjects only).

Additional blood and urine samples may be taken or vital signs and ECGs recorded at the discretion of the investigators.

Additionally, emergence of suicidal ideation will be assessed using the Colombia suicide severity rating scale (C-SSRS) at screening, and during each study visit. Arizona Sexual Experiences (ASEX) will be used to document sexual dysfunction and the Karolinska Sleepiness Scale (KSS) will be used to document sleepiness/sedation.

STATISTICAL METHODS

Sample size determination

The sample size for the study is determined based on the assumption of a treatment effect size of 0.45 in the mean change from baseline (Visit 2) in MADRS total score between JNJ-67953964 treatment group and placebo. The assumed effect size is based on review of the literature looking at the adjunctive treatment with ALKS 5461, a combination of buprenorphine (partial μ -opioid receptor agonist and KOR antagonist) and samidorphan (a potent μ -opioid receptor antagonist) in MDD patients with an inadequate response to one or two courses of an antidepressant (Fava 2016 and Enrich 2015).

Using the data from the same studies, an estimate of 11 for standard deviation in the change in MADRS total score from baseline was made. Detection of 0.45 effect size with a power of 90% at an overall 1-sided significance level of 0.20, requires 45 subjects in each treatment group (90 subjects in total).

When adjusted for a drop-out rate of approximately 5% of subjects during the treatment period, the required number of subjects to be randomized is 96. To achieve this, the estimated number of subjects to enter the lead in period is 142, after adjusting for an estimated placebo response rate of 25% and drop-out rate of 10% during the lead-in period.

A blinded sample size re-estimation is anticipated with 180 as the maximal number of subjects to be enrolled in the trial.

Efficacy analysis

Primary

Primary efficacy analyses will be based on the intention-to-treat analysis set from enriched population (eITT) which consists of randomized lead-in placebo non-responders receiving at least one dose of study medication and having at least one post-treatment baseline efficacy measurement.

The JNJ-67953964 treatment group will be compared with placebo using the primary efficacy endpoint: change from treatment baseline in MADRS score during the treatment period. The comparison will be performed by means of a mixed-effects model for repeated measures (MMRM), with time, treatment (placebo, JNJ-67953964) and time-by-treatment interaction as factors and baseline total MADRS score as a continuous covariate. Other covariates of interest may be included in the MMRM model. The treatment-placebo differences will be obtained using the appropriate contrast in the MMRM models at the 6-week endpoint.

Descriptive statistics for actual values and changes from baseline for MADRS Score at each time point of the double-blind treatment phase will be provided by treatment group using both: eITT and fITT analysis sets. Mean differences between the treatments with corresponding confidence intervals (CIs) will be reported.

Frequency tables for response and remission of depressive symptoms (derived from the MADRS) will be provided by treatment group at each time point of the double-blind treatment phase using both: eITT and fITT analysis sets. Chi square test to test the overall differences between the treatment groups will be performed.

Secondary

Evaluation of Anhedonia

Change from treatment baseline in SHAPS score during the treatment period will be analyzed with the same MMRM model as primary efficacy variable (MADRS) using both: eITT and fITT analysis sets. The JNJ-67953964 treatment group will be compared with placebo using the appropriate contrast in the MMRM model at the 6-week endpoint.

The effect of JNJ-67953964 on depression symptoms across different baseline levels of anhedonia will be explored. Descriptive statistics for actual values and changes from baseline in MADRS Score within different anhedonia levels (no anhedonia, low level of anhedonia and high level of anhedonia; cutoff values will be provided in Statistical Analysis Plan) will be presented by treatment group using both: eITT and fITT analysis set.

Evaluation of Depression

Descriptive statistics for actual values and changes from baseline for CGI-S and SMDDS (total) scores at each time point of the double-blind treatment phase will be provided by treatment group using both: eITT and fITT analysis sets. In addition, for CGI, frequency tables will be provided by treatment and time-point.

Evaluation of Anxiety

Descriptive statistics for actual values and changes from baseline for SIGH-A total score as well as HAM-A₆ score at each time point of the double-blind treatment phase will be provided by treatment group using both: eITT and fITT analysis sets. Mean differences between the treatments with corresponding confidence intervals (CIs) will be reported.

Exploratory

Cognitive Functioning Analysis

The actual values of CPFQ and changes from baseline will be summarized at each scheduled time point by treatment. These analyses will be performed on both: eITT and fITT analysis sets.

Biomarker Analyses

Biomarker levels will be tabulated for each time point and summary statistics will be calculated. Posttreatment changes in biomarker levels will be assessed by treatment group. Analysis of variance (ANOVA) and t-test will be used to assess differences across groups and time points. Correlations between biomarker levels and clinical endpoints will be evaluated.

All biomarker data obtained from this study may also be included in an ongoing cross-study analysis to investigate the relationship between depression severity, phenotypes, and biomarkers.

Pharmacokinetic Analyses

Plasma concentrations for JNJ-67953964 will be analyzed. Based on the individual plasma concentration-time data from all subjects, exposure parameters of JNJ-67953964 will be derived using population PK (popPK) modeling. Potential baseline covariates (eg, demographics such as age, sex and race, body weight, laboratory variables such as creatinine clearance, etc.) may be included in the models, if relevant. The following exposure parameters will be derived using Bayesian feedback analysis: AUC_{24h} and C_{0h}. Results will be tabulated and summary statistics will be generated. Individual plasma concentrations per study visit will be listed. Pharmacokinetic and pharmacodynamic relationship will be explored, if feasible. Details of population PK analysis and PK/PD analysis will be given in an analysis plan and the results will be presented in a separate report.

Safety analyses

Statistical analysis of the safety data will be done by the sponsor or under the authority of the sponsor. Specific details will be provided in the Statistical Analysis Plan.

All subjects receiving at least one dose of study drug will be included in the safety analysis.

AEs will be coded using the current version of Medical Dictionary for Regulatory Activities (MedDRA). All reported AEs with onset during the double-blind treatment phase (i.e., treatment-emergent adverse events [TEAEs], and AEs that have worsened since baseline) will be included in the analysis. Serious adverse events (SAEs) will be summarized separately.

Laboratory data will be summarized by type of laboratory test and treatment. Descriptive statistics will be calculated for each laboratory analyte at baseline and at each scheduled time point, and for changes from baseline. The percentage of subjects with values out of normal limits will be summarized. Data listings of subjects with at least one abnormal value will be provided.

Descriptive statistics of pulse, supine blood pressure (systolic and diastolic), temperature and body weight values and changes from baseline will be summarized at each scheduled time point by treatment. The percentage of subjects with values beyond clinically important limits will be summarized. Data listings of subjects with at least one abnormal value will be provided.

Heart rate and ECG intervals (RR, PR, QRS and QT), corrected QT intervals according to Bazett's formula (QTcB) and Fridericia's formula (QTcF) and changes from baseline will be summarized at each scheduled time point using descriptive statistics. The number and percentage of subjects with at least one occurrence of a treatment-emergent potentially clinically important QTc measurement (QTc value >450 , >480 , or >500 msec) or with a change from baseline in QTc >30 msec or 60 msec, will be summarized by treatment group. Data listings of subjects with any potentially clinically important values or with a change from baseline in QTc will be provided.

Subjects with abnormal physical and neurological examination findings will be presented in a data listing.

The suicidal ideation and behavior data collected from the C-SSRS will be summarized descriptively at each scheduled timepoint by treatment group. Data from the subjects with suicidal ideation and behavior will be presented in data listing. ASEX and KSS data collected will be summarized descriptively at each scheduled timepoint by treatment group. All the data will be listed.

Interim Analysis

An interim analysis may be executed. The procedures for the interim analysis will be described in a separate charter.

A blinded data review for purpose of sample size re-estimation may be performed during the study after minimally 50% of the subjects are randomized and have completed Week 6 of the double-blind treatment period. Sample size may be re-adjusted if the observed SD substantially deviates from the hypothesized SD or if the lead-in response and dropout rate substantially deviate from the assumed values. The maximal number of subjects to be enrolled in the trial will not surpass 180.

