9.2. Efficacy Analyses

9.2.1. Primary

Primary efficacy analyses will be based on the intention-to-treat analysis set from enriched population (eITT) which consists of randomized lead-in placebo non-responders receiving at least one dose of study medication and having at least one post-treatment baseline efficacy measurement.

The JNJ-67953964 treatment group will be compared with placebo using the primary efficacy endpoint: change from treatment baseline in MADRS score during the treatment period. The comparison will be performed by means of a mixed-effects model for repeated measures

(MMRM), with time, treatment (placebo, JNJ-67953964) and time-by-treatment interaction as factors and baseline total MADRS score as a continuous covariate. Other covariates of interest may be included in the MMRM model. The treatment-placebo differences will be obtained using the appropriate contrast in the MMRM models at the 6-week endpoint.

Sensitivity analyses of the primary endpoint will be performed using an analysis of covariance (ANCOVA) model; these will be detailed further in the Statistical Analysis Plan.

In addition, same MMRM model will be fitted on full intention-to-treat analysis (fITT) set consisting of all the randomized subjects receiving at least one dose of study medication and having at least one post-treatment baseline efficacy measurement.

Missing data mechanisms exploration and possible imputation methods for primary efficacy variable will be described in detail in Statistical Analysis Plan.

Descriptive statistics for actual values and changes from baseline for MADRS Score at each time point of the double-blind treatment phase will be provided by treatment group using both: eITT and fITT analysis sets. Mean differences between the treatments with corresponding confidence intervals (CIs) will be reported.

Frequency tables for response and remission of depressive symptoms (derived from the MADRS) will be provided by treatment group at each time point of the double-blind treatment phase using both: eITT and fITT analysis sets. Chi square test to test the overall differences between the treatment groups will be performed.

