9.2.2. Secondary

Evaluation of Anhedonia

Change from treatment baseline in SHAPS score during the treatment period will be analyzed with the same MMRM model as primary efficacy variable (MADRS) using both: eITT and fITT analysis sets. The JNJ-67953964 treatment group will be compared with placebo using the appropriate contrast in the MMRM model at the 6-week endpoint.

Descriptive statistics for actual values and changes from baseline for SHAPS total score at each time point of the double-blind treatment phase will be provided by treatment group using both: eITT and fITT analysis sets. Mean differences between the treatments with corresponding CIs will be reported.

The effect of JNJ-67953964 on depression symptoms across different baseline levels of anhedonia will be explored. Descriptive statistics for actual values and changes from baseline in MADRS Score within different anhedonia levels (no anhedonia, low level of anhedonia and high level of anhedonia; cutoff values will be provided in Statistical Analysis Plan) will be presented by treatment group using both: eITT and fITT analysis set.

Evaluation of Depression

Descriptive statistics for actual values and changes from baseline for CGI-S, SATE and SMDDS (total) scores at each time point of the double-blind treatment phase will be provided by treatment group using both: eITT and fITT analysis sets. In addition, for CGI-S, frequency tables will be provided by treatment and time-point.

Evaluation of Anxiety

Descriptive statistics for actual values and changes from baseline for SIGH-A total score as well as HAM-A₆ score at each time point of the double-blind treatment phase will be provided by treatment group using both: eITT and fITT analysis sets. Mean differences between the treatments with corresponding CIs will be reported.

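### The primary MMRM as written uses one baseline-MADRS slope for every treatment visit, which can cost some precision in the Week 6 contrast; adding baseline-by-time is cheap.

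*Protocol*

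**What the plan says.** Protocol 9.2.1 specifies an MMRM on change from treatment baseline in MADRS, with time, treatment, "time-by-treatment interaction as factors and baseline total MADRS score as a continuous covariate". The synopsis has the same list: time, "treatment (placebo, JNJ-67953964) and time-by-treatment interaction as factors and baseline total MADRS score as a continuous covariate". The primary contrast is drug against placebo at the 6-week endpoint. Both places allow further covariates without naming them. Section 9.2.1 adds an ANCOVA sensitivity analysis and leaves its details to the Statistical Analysis Plan. Section 9.2.2 carries the same MMRM over to SHAPS.

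The sample size rests on the "assumption of a treatment effect size of 0.45 in the mean change from baseline (Visit 2) in MADRS total score", and for the SD the synopsis says that "an estimate of 11 for standard deviation in the change in MADRS total score from baseline was made".

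The SAP supplied is the population PK and PK/PD plan. It does not specify the primary MMRM. Neither document states the MMRM covariance structure, the SD of MADRS at treatment baseline, the SDs by visit or the correlations between visits.

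**The concern.** With baseline as a main effect only, the regression of change on baseline is constrained to be equal at all post-baseline treatment visits. SAP 4.6 places these at treatment Weeks 1, 3, 4, 5 and 6. If later scores decorrelate from baseline, that slope becomes more negative with time. A common slope is a weighted average of the visit slopes. Where residual variance grows over the weeks and the covariance model allows it, the weight falls mainly on the early visits.

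The Week 6 contrast would then be adjusted with a slope that is too shallow, and would keep variance that the recorded baseline could have removed. What is at stake is precision at the decision visit.

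**Working it through.** **1. The plan's own figure.** n per arm = 2(z₀.₈₀ + z₀.₉₀)²/d² = 2(0.8416 + 1.2816)²/0.45² = 9.016/0.2025 = 44.5, so 45, as stated. Power at 45 is Φ(0.45√22.5 − 0.8416) = Φ(1.293) = 90.2%. The planned difference is 0.45 × 11 = 4.95 points. This is a two-sample calculation on change scores with no baseline adjustment.

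**2. Formula.** With complete data, let b_j be the slope of change on baseline at visit j, σ₀ the baseline SD and σ₆ the Week 6 residual SD given baseline.

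- Common slope: b_c = Σ w_j b_j, with weights w proportional to Σ⁻¹1, where Σ is the residual covariance under the common-slope model.
- Week 6 variance inflation against visit-specific slopes: (b₆ − b_c)² σ₀² / σ₆².

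**3. One scenario in full.** Assumed, not from the documents: MADRS SD 6 at treatment baseline rising linearly to 11 at Week 6, correlation 0.794 per week, unstructured covariance.

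- Correlation of baseline with Week 6: 0.794⁶ = 0.251. Then b₆ = 0.251 × 11/6 − 1 = −0.54. At Week 1, b₁ = 0.794 × 6.83/6 − 1 = −0.10.
- σ₆ = 11√(1 − 0.251²) = 10.65. The SD of change is √(10.65² + 0.541² × 36) = 11.1, close to the protocol's 11.
- Week 1 carries 0.89 of the weight, so b_c = −0.133.
- Inflation = (0.541 − 0.133)² × 36/10.65² = 5.3%.

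**4. Simulation of five scenarios** (45 per arm, unstructured covariance, 3,000 trials each):

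| Assumed MADRS SD, baseline to Week 6 | Week 6 variance, common / visit-specific |
|---|---|
| 6 to 11, correlation 0.794/week | 1.041 |
| 5 to 11 | 1.033 |
| 7 to 11, correlation 0.80/week | 1.056 |
| with 20% stable between-patient share | 1.013 |
| with 40% stable between-patient share | 0.989 |

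A repeat gave 1.04, 1.00, 1.06, 1.01 and 0.99, so the ratios are good only to about 0.03.

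**5. Slopes and variances set directly.** Assumed: baseline SD 4 to 6, Week 6 residual SD 10.7, autoregressive correlation 0.88 per week. Inflation by the formula in step 2:

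| Slope, Week 1 to Week 6 | Residual SD growing from 5 to 10.7 | Residual SD constant |
|---|---|---|
| equal | 0% | 0% |
| −0.15 to −0.35 | 0.7–1.5% | 0.1–0.3% |
| −0.10 to −0.45 | 2.0–4.4% | 0.4–0.9% |
| 0 to −0.60 | 5.7–12.9% | 1.3–2.8% |

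Simulated ratios over this grid ran from 0.99 to 1.13, and mean error was essentially zero in both models. With equal slopes the common slope gained at most about 1%. With constant residual SD, Weeks 1 and 6 carried 0.43 and 0.40 of the weight, so dominance of early visits depends on residual variance that grows.

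A constant raw MADRS SD of 6 with correlation 0.8 per week gives a larger inflation (about 18% by formula, 1.17 simulated). However, it implies a change SD of only √(72 × (1 − 0.8⁶)) = 7.3, well below the planned 11.

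**6. Baseline imbalance is the same effect.** In the step 3 scenario, one standard error of baseline difference is 6√(2/45) = 1.26 points. It moves the Week 6 difference by 1.26 × 0.408 = 0.52 points. The Week 6 standard error is 10.65√(2/45) = 2.24, so the shift is 0.23 SE, and 0.23² = 5.3%, the inflation already counted.

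**7. Power for 4.95 points.** In step 3, the common slope gives Φ(4.95/(2.245√1.053) − 0.842) = 90.4%, and visit-specific slopes give Φ(4.95/2.245 − 0.842) = 91.4%. For the SD 7 to 11 scenario the figures are 90.2% and 91.5%.

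**The case against.** The strongest case against acting is that both specifications are valid and unbiased, and that every input to the loss is assumed. The only error structure the documents give for MADRS change is in SAP 4.6: a subject random effect plus uncorrelated residuals, which is compound symmetry. Equal visit weights then apply. With the step 3 slopes (−0.10, −0.29, −0.38, −0.47, −0.54; mean −0.36) the inflation is only (0.541 − 0.355)² × 36/10.65² = 1.1%, about what the extra term may cost. Moreover, the protocol permits other covariates, a single-visit Week 6 ANCOVA would use a Week 6 slope, and an efficacy analysis plan outside the supplied documents may already include the interaction.

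Most of this stands as a limit on size. It does not remove the point. SAP 4.6 concerns a different analysis. The permission for further covariates, if it covers the interaction at all, leaves a choice about the primary test open. The ANCOVA's form is not given, and it does not change the primary model.

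A reader might infer three stronger things, none of which the documents support:

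- **That the Week 6 slope is in fact fitted mainly to Week 1 and a loss of several percent is certain.** This needs steepening slopes and a heterogeneous covariance, and neither is stated.
- **That the estimate is biased when the arms differ at baseline.** The shift is conditional on the realised imbalance, averages to zero over randomizations, and is the variance loss seen another way.
- **That the trial is underpowered.** The 45 per arm takes no credit for baseline adjustment, and step 7 stays above 90% with the common slope.

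**Conclusion.** The point holds as a minor matter of efficiency. The stated model has a single baseline slope although treatment varies by visit and the decision is taken at Week 6. Relative to visit-specific slopes, Week 6 variance is about −1% to +6% in the five scenarios, up to about 13% in the strong-drift grid, and no higher if the slopes are equal. These figures rest on assumed SDs, correlations and covariance structure, with complete data; the upper end should not be read as the expected loss. The case for change is the asymmetry: the term can recover several percent, and costs about 1% at worst.

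**What to change.** In the synopsis and 9.2.1, before unblinding, list the MMRM fixed effects as time, treatment, time-by-treatment, baseline MADRS and baseline MADRS-by-time. In the SHAPS model of 9.2.2, let the baseline term vary by time in the same way. State the covariance structure in the same edit, since the size of the effect depends on it. If an efficacy analysis plan already includes the interaction, align the protocol with it.

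The cost is one model term: 4 degrees of freedom with five visits, or at most about 1% of Week 6 variance if the slopes are flat. No extra data, visits or subjects are needed, and the sample size stays as it is.
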